## 2 TRIAL DESIGN

CEDAR is a dual endpoint, dose escalation phase I trial using a time to event continual reassessment method (TITE CRM). Response and Toxicity endpoints will be combined via dose escalation rules to identify the optimal dose schedule. At most, 30 patients will be recruited to the trial.

Dose escalation will be achieved by first increasing the frequency of administration of enadenotucirev followed by increasing the dose of enadenotucirev as detailed in the trial flow chart. These dose schedules are considered ordered with increasing toxicity expected from one dose schedule to the next.

See section 8 and 17.2 for further details.

## 3 OBJECTIVES AND ENDPOINTS

Primary Objective	Endpoints/ Outcome measures	Time point(s) of evaluation of this end point

 
Determine the optimal dose and frequency of enadenotucirev that can be administered with chemoradiation
 
	
 
Dose limiting toxicity
 
MRI tumour regression grade
 
	
 
From Day 1 to Week 13
 
Week 13
 

Secondary Objectives	Endpoints	

 
Ability to deliver enadenotucirev concurrently with chemoradiation
 
	
 
Treatment tolerance measured by proportion of patients completing at least 80% of the intended Capecitabine dose and at least 20 fractions of radiotherapy
 
	
 
Week 9
 

 
To measure local response rate to combined therapy compared to pre-treatment status
 
	
 
MRI tumour regression grade
 
Pathological complete response
 
Neoadjuvant Rectal (NAR) score
 
	
 
Week 13
 
Post resection
 
Post resection
 

Tertiary/Exploratory Objectives	Endpoints	

 
To identify 'proof of concept' that enadenotucirev replicates in the tumour
 
	
 
IHC staining of hexon protein coat, viral gDNA and viral mRNA gene expression in tumour cells
 
	
 
Archival tumour tissue
 
Week 4 biopsy
 
Resection sample
 

 
To analyse gene expression changes in rectal cancer in response to enadenotucirev
 
	
 
Whole genome RNA expression via RNA sequencing/ Nanostring gene expression analysis
 
	
 
Archival tumour tissue
 
Week 4 biopsy
 
Resection sample
 


 
Analyse changes in circulating tumour DNA in response to chemoradiation and enad
 
	
 
ctDNA analysis exploring clearance of ctDNA and any/or emerging changes in persisting ctDNA
 
	
 
Baseline (Pre 1st loading dose)
 
Week 4
 
Week 13
 
4-6 weeks post-surgery
 

 
Assess the changes in microbiome taxa during therapy
 
	
 
Extraction of DNA and 16S sequencing and meta-transcriptomics from faecal samples
 
	
 
Baseline (pre-enad)
 
End of week 1 / 2
 
End of week 4
 
End of week 7
 
Week 13
 

 
Analyse the immune microenvironment as evidenced by immune cell infiltrates
 
	
 
Multiplex Immunohistochemistry of immune cell markers
 
	
 
Archival tumour tissue
 
Week 4 biopsy
 
Resection sample
 

## 4 PATIENT SELECTION

Written informed consent must be obtained before any trial specific procedures are performed. The Investigator will determine patient eligibility based on the following criteria.

### 4.1 Eligibility criteria

#### ***Inclusion criteria:***

A patient will be eligible for inclusion in this trial if all of the following criteria apply.

1. Histologically confirmed invasive adenocarcinoma of the rectum.
2. Locally advanced colorectal cancer as defined by pelvic MRI with a threatened circumferential resection margin (cT3mr+ve), or inclusion of an adjacent organ, or low tumours at/below the level of the levators or enlarged pelvic side wall nodes or selected by the multidisciplinary team MDT for treatment with neoadjuvant (chemo)radiotherapy, regardless of TNM classification
3. Patients with oligometastatic disease suitable for radical treatment are permitted provided that the site specific MDT deems them suitable for chemoradiation
4. Male or female, Age  $\geq 18$  years.
5. ECOG performance score of 0 - 1
6. The patient is willing and able to comply with the protocol scheduled biopsy, follow-up visits and examinations for the duration of the trial.
7. Written (signed and dated) informed consent.
8. Adequate renal function demonstrated by:
  - Creatinine  $\leq 1.5$  ULN and estimated glomerular filtration rate (eGFR)  $\geq 60$  mL/min/1.73m^2 (or measured creatinine clearance  $\geq 60$  mL/min)  
**and**
  - Urine dipstick for proteinuria at screening and baseline negative or trace. Patients may be included with results of 1+ if they have a spot urinary albumin creatinine ratio (ACR) of either:
    - (i)  $\leq 3$  mg/mmol **or**
    - (ii)  $>3$  mg/mmol with a 24 hour urinary protein  $<1.0$  g/24hours  
**and**
  - Serum complement components C3 and C4 within the normal range
9. Haematological and biochemical indices within the ranges shown below:

Lab Test	Value required
Haemoglobin (Hb)	$\geq 90$ g/L
Absolute neutrophil count	$\geq 1.5 \times 10^9$ /L
Platelet count	$\geq 100 \times 10^9$ /L
Bilirubin	$< 1.5$ upper limit of normal
Aspartate transaminase and/or alanine transaminase	$\leq 3$ x upper limit of normal
INR	$\leq 1.5$
aPTT	Within laboratory normal range

#### ***Exclusion criteria:***

A patient will not be eligible for the trial if any of the following apply:

1. Pregnant or breast-feeding women, or women of childbearing potential unless effective methods of contraception are used.
2. Pulmonary lymphangitis (if metastatic disease present)
3. Past medical history:
  - a. Known history or evidence of significant immunodeficiency due to underlying illness and/or medication (e.g. systemic corticosteroids, or other immunosuppressive medications including cyclosporine, azathioprine, interferons in the 4 weeks before the first dose of trial treatment)
  - b. Splenectomy
  - c. Prior allogeneic or autologous bone marrow or organ transplantation

- d. Patients with a history of, or active, known or suspected auto-immune disease or a syndrome that requires systemic or immunosuppressive agents; patients with vitiligo, type I diabetes mellitus, residual hypothyroidism due to autoimmune disease only requiring hormone replacement, psoriasis not requiring systemic treatment or conditions not expected to recur in the absence of an external trigger are permitted to enrol
- e. History of idiopathic pulmonary fibrosis, drug-induced pneumonitis, or evidence of active pneumonia or pneumonitis on computed tomography scan
- f. Active viral disease or known positive serology for HIV, hepatitis B or hepatitis C
- g. Active infections requiring antibiotics, physician monitoring, or recurrent fevers  $>38.0^{\circ}\text{C}$  associated with a clinical diagnosis of active infection
- h. Prior pelvic radiotherapy
- i. Any other active malignancy, with the exception of adequately treated cone-biopsied *in situ* carcinoma of the cervix uteri and non-melanoma skin lesions.
- j. Uncontrolled cardiorespiratory comorbidity (e.g. severe pulmonary fibrosis, inadequately controlled angina or myocardial infarction in the last 6 months)
- k. Major disturbance in bowel function (e.g. severe incontinence, Crohn's disease,  $>6$  loperamide/day), risk of bowel obstruction due to tumour- exception defunctioning colostomy performed
- l. Treatment with any COVID-19 vaccine in the 28 days before the first dose of enadenotucirev, unless the vaccine is known to not be based on an adenoviral vector (e.g. mRNA vaccines)
- m. Treatment with any vaccine (including known non-adenoviral COVID-19 vaccines) in the 7 days before first dose of enadenotucirev

- 4. Use of the following antiviral agents: ribavirin, adefovir, lamivudine or cidofovir within 7 days prior to the first dose of trial treatment; or pegylated interferon in the 14 days before the first dose of trial treatment
- 5. Treatment with any other investigational agent, or participation in another interventional clinical trial within 28 days prior to enrolment. In follow up for an interventional trials and observational studies are allowed
- 6. History of DVT or pulmonary embolus in the 12 months before the first dose of study treatment
- 7. History of significant bleeding requiring hospitalisation in the 12 months before the first dose of study treatment
- 8. Patients receiving therapeutic or prophylactic anticoagulation therapy
- 9. Known dihydropyrimidine dehydrogenase (DPYD) deficiency
- 10. Prior chemotherapy is allowed as long as  $>28$  days since the last administration and any toxicity has resolved to NCI CTCAE grade 1 or less
- 11. Other psychological, social or medical condition, physical examination finding or a laboratory abnormality that the Investigator considers would make the patient a poor trial candidate or could interfere with protocol compliance or the interpretation of trial results.

## 4.2 Protocol deviations and waivers to entry criteria

Protocol adherence is a fundamental part of the conduct of a clinical trial. Changes to the approved protocol need prior approval unless for urgent safety reasons.

Investigators must contact OCTO to obtain guidance and/or clarification as necessary if unsure whether the patient satisfies all the entry criteria and to clarify matters of clinical discretion. OCTO will contact the chief investigator or clinical coordinators as necessary.

**Investigators should not request a protocol waiver to enter a patient who does not satisfy the inclusion and exclusion criteria.**

The investigator must document and explain any deviations from the approved protocol. The investigator should promptly report any important deviations that might impact patient safety, data integrity or be a possible serious breach (see 23.7 below) to the trial office.

## 4.3 Re-screening if patient does not meet inclusion/exclusion criteria first time round

Screen failures are ineligible and will not be rescreened unless imaging is not within the required timeframe - this should be repeated and patient reconsidered for the trial.

#### 4.4 Patient registration procedure

The site must contact OCTO to check the availability of a screening slot and if available reserve the slot prior to giving out a Patient Information Sheet. A screening number should be requested prior to screening the patient and the site should register the participant within 2 weeks of receiving the screening number or relinquish the slot unless an extension is agreed with the trial office.

Before entering a patient onto the trial, the Principal Investigator or designee will confirm eligibility. If in any doubt the Chief Investigator must be consulted before entering the patient. Details of the query and outcome of the decision must be documented on the registration/ eligibility checklist. **Protocol waivers should not be requested to enter patients who are not eligible.**

Site staff will complete the trial Registration Form and email the form to the Trial Office to further confirm the patient's eligibility. The original Registration Form should be retained at site.

A Screening Log must be kept of all patients considered for the trial including any that are subsequently excluded; the reason for exclusion must be recorded on this form. A copy of the Screening Log must be sent to the trial office on request, but without patient identifiers. The original log must be retained on site in the ISF.

##### To register a patient:

After checking patient eligibility site staff will complete the trial Registration Form. Scan the Registration Form and email to: [[contact]](mailto:[contact])

The trial office will check the submitted form and register the patient on the trial. Confirmation of the patient's trial number will be emailed to the PI & other relevant site contacts.

Enadenotucirev dosing schedule assignment will be determined pre-registration and confirmed by email to the PI & other relevant site contacts. See sections 8.2 and 17.2 for information on dosing schedules and dosing group decisions.

## 5 TRIAL ASSESSMENTS AND PROCEDURES

Please refer to the Schedule of Events given at the front of this protocol. Details of all protocol evaluations and investigations must be recorded in the patient's medical record for extraction onto the CRF.

### 5.1 Informed consent

Potential participants will be given a current, approved version of the Patient Information Sheet and Consent Form. They will also receive clear verbal information about the trial detailing no less than: the nature of the trial; the implications and constraints of the protocol; the known side effects and any risks involved in taking part. It will be explained that they will be free to withdraw from the trial at any time, for any reason, without prejudice to future care, and with no obligation to give a reason for withdrawal. They will have at least 24 hours to consider the information provided and the opportunity to question the Investigator, their GP or other independent parties before deciding whether to participate. Once registered onto the trial, the patients GP will be notified via a letter with specific consent for this process being obtained.

The Investigator who obtains consent must be suitably qualified and experienced. All delegates must be authorised by the Principal Investigator to obtain consent. The Investigator is responsible for ensuring that the trial consent procedures comply with current applicable GCP Regulatory and ethical requirements. Informed consent discussions and outcomes must be well documented in the medical record. The Investigator must be satisfied that the patient has made an informed decision before taking consent. The patient and the Investigator must personally sign and date the current approved version of the Informed Consent Form in each other's presence. A copy of the Patient Information Sheet and signed Consent Form will be given to the participant. The original signed form will be retained at the trial site, ideally in the Investigator Site File (if local policy permits) and one copy held in the medical records. When required, a copy will also be provided to the tissue bank to evidence consent for storage of samples.

***Contraceptive/ Pregnancy counselling***

All participants must be advised on the need to use reliable methods of contraception during the trial. The advice should include:

- (1) The acceptable methods, including: male or female sterilization, implants, injectables, combined oral contraceptives, some intrauterine devices (IUDs), and abstinence.
- (2) The recommendation that a barrier method should be used in addition to another form of contraception.
- (3) Males should continue to take these precautions for a minimum 6 months after the last dose of trial drug.
- (4) Females should continue to take these precautions a minimum of 6 months after the last dose of trial drug.
- (5) That any pregnancy (also applies to females partners of male trial subjects) occurring within 6 months of the last administration of trial drug will be followed up and the outcome of all pregnancies (spontaneous miscarriage, elective termination, normal birth or congenital abnormality) will be reported and followed up even if participant is discontinued from the trial.

**5.2 Screening/Baseline evaluations**

Potential participants will be identified by their existing clinical care team at surgical clinics, oncological clinics or multidisciplinary team meetings. Local clinical teams can confirm they are potential eligible for the trial and can therefore be approached. After the patient has been approached and deemed potentially eligible, the following screening and eligibility assessments must be performed/ obtained within the 2 weeks before the patient receives the first trial dose (with the exceptions of CT & MRI which must be within 62 & 42 days of start of treatment respectively, and standard of care tests which have been done, before consent, but within 21 days before the first treatment day).

- Written informed consent
- Demographic details including age, gender
- Medical History to include cancer history, prior cancer therapies and procedures, reproductive status, and clinically significant disease history and concomitant diseases.
- Concomitant medications (including prescription drugs, over-the-counter drugs, herbal/ homeopathic remedies, nutritional supplements) used by the subject within 14 days before the start of trial treatment
- Complete physical examination to include lungs, abdomen, heart and symptom driven examination. Any abnormality identified at baseline should be recorded
- Height, weight and body surface area (BSA)
- ECOG performance status
- Vital signs: systolic / diastolic blood pressure (BP), pulse rate, respiratory rate and temperature.
- Screening blood tests:
  - Haematology – Hb, white blood cells (WBC) with differential count (neutrophils and lymphocytes) and platelets
  - Biochemistry – sodium, potassium, calcium, phosphate, urea, creatinine, total protein, albumin, bilirubin, alkaline phosphatase (alk phos), AST and/or ALT and LDH
  - Coagulation screen (aPTT and INR)
- Pregnancy test (females of childbearing potential only): serum or urine Human Chorionic Gonadotropin (HCG) test to rule out pregnancy at trial entry; results must be obtained and reviewed before the first dose of IMP is administered.
- Electrocardiogram (ECG)
- Dihydropyrimidine dehydrogenase (DPYD) deficiency test (any time before trial enrolment)
- Urine dipstick for protein
- Confirm histological diagnosis from pathology report
- CT chest/ abdomen/ pelvis- diagnostic CT may be used if within 62 days of first trial dose. Repeat CT to be scheduled within 14 days of informed consent, if > 62 days. Whole body PET-CT is an acceptable alternative.
- Pelvic MRI- diagnostic MRI may be used if within 42 days of first trial dose. Repeat MRI to be scheduled within 14 days of informed consent if > 42 days.
- Investigational blood sample (after informed consent)
- Faecal sample collection & diet questionnaire (collected at patients' home after informed consent (optional) and before 1st dose of enadenotucirev – not applicable to all participating sites)

Results of standard-of-care tests or examinations performed before obtaining informed consent and within 21 days before the start of trial treatment may be used; such tests do not need to be repeated for screening.

All screening evaluations must be completed and reviewed to confirm that subjects meet all eligibility criteria before the first dose of trial treatment. The Investigator will maintain a screening log to record details of all subjects screened and to confirm eligibility or record reasons for screening failure, as applicable.

The CRF will only be completed for those subjects who are eligible for the trial and then subsequently registered. At the time of enrolment, each eligible subject will be assigned a unique subject number and the next sequential number to be allocated.

Also, pre dose assessments (section 5.3.1) need to be taken within 72 hours prior to first loading dose at the start of week 1.

It is recommended that the investigational blood sample is taken during a regularly scheduled visit such as the planning CT appointment to minimise extra visits. However, it can be done at any stage prior to the first dose of enadenotucirev.

### 5.3 Pre-treatment evaluation

Evaluation schedule A applies to all patients prior to day 1 of any dose or sequence of treatment.

The table below summarises what pre dose evaluations (schedule A or B) should be undertaken for each patient on any given day, depending on which dosing group they are assigned to (Section 8.2 and 17.2 for more information). Loading and after loading doses of enadenotucirev should be given on 3 non-consecutive days over a 7-day period during weeks 1-2-and 8-9 (e.g. Mon, Wed, Fri **or** Fri, Mon, Wed **or** other convenient schedule). Doses given during the 1st week of chemoradiation should be given on day 1 and day 5. On each dosing day the following assessments are required:

#### Dosing group 1-4

	Dosing Day 1	Dosing Day 2	Dosing Day 3
Week 1/2	A	B	A

#### Dosing group 4

	Dosing Day 1 (Day 1 CRT)	Dosing Day 2 (Day 5 CRT)
Week 3	A	A

#### Dosing groups 2, 3 & 4

	Dosing Day 1	Dosing Day 2	Dosing Day 3
Week 8/9	A	B	A

#### 5.3.1 Evaluation schedule A

**Pre- Dose – the following assessments can be completed within 72 hours prior to the dose. Vital signs to be completed on day of dosing**

- Adverse events and DLTs since the previous assessment
- New or changes to existing medications
- Physical examination of major body systems
- Weight
- ECOG performance status
- Local laboratory assessments:
  - Urine dipstick – if 2+ or greater proteinuria enadenotucirev dosing should be interrupted pending completion of 24 hour urine collection to exclude significant proteinuria, see further guidance in section 9.3.

- Routine blood samples
  - Haematology – Hb, white blood cells (WBC) with differential count (neutrophils and lymphocytes) and platelets
  - Biochemistry – sodium, potassium, calcium, phosphate, urea, creatinine, total protein, albumin, bilirubin, alkaline phosphatase (alk phos), AST and/or ALT and LDH
  - Coagulation screen (aPTT and INR)

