Two similar events had also been reported in the completed study of enadenotucirev monotherapy (Study ColoAd1-1001). Review of the available data from the 61 patients treated in this study appears to indicate two separate time periods following enadenotucirev administration when there are discernible effects on renal function (although the majority of these are noted to not have been considered of clinical significance or reported as adverse events). The first in the acute period following dosing (on Days 1, 3, 5) where proteinuria, reduction in albumin, reduction in blood pressure and reduced renal function are likely to be related to cytokine-mediated vascular leakage, in turn recovering over time. In some subjects, similar findings occur around Day 21 onwards, again, in most cases, resolving over time. The latter appear not to be related to dose or schedule.

In the overall context of three patients out of 100 treated with intravenous enadenotucirev presenting with significant renal injury, the measures that have been and are to be implemented in the on-going studies of enadenotucirev are considered appropriate to managing the potential risk to patients in the context of treatment of their underlying disease. These measures, excluding those considered broadly to be at increased risk of renal injury, serve to identify any decline in renal function quickly with a view to implementing early intervention to any renal injury to in turn limit the damage of any recurrence of such an event

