**5.3.2 Evaluation schedule B*****Pre-Dose***

- Adverse events and DLTs since the previous assessment
- New or changes to existing medications
- Physical examination of major body systems
- Vital sign measurements: systolic / diastolic blood pressure (BP), pulse rate, respiratory rate and temperature
- Weight
- ECOG performance status

It is recommended that subjects also receive antipyretic prophylaxis, steroid prophylaxis and hydration at the time of each injection of enadenotucirev (See section 8.3). The recommended regime is:

- 1 hour prior to administration
  - IV hydrocortisone 100mg
  - PO Paracetamol 1000mg

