**Renal injury:** Three patients out of 123 patients (2.4%) have developed significant renal impairment while receiving enadenotucirev. Whilst no confirmed pathophysiology has been identified it is felt to be due to vascular leakage due to cytokine release. Proteinuria of 2+ on a urine dipstick should therefore be further investigated, due to the potential risk of serious renal injury, with 24 hour urine collection for protein/creatinine ratio. If preferable locally, a urine protein- to-creatinine ratio or urine albumin – to – creatinine ratio are also acceptable in lieu of a 24 hour collection test. Additional blood tests should also be up to date including a serum albumin and serum creatinine. A consultation with nephrology is advised for specialist input. Specifically, early specialist intervention for investigation and treatment if decline in renal function is detected will include:

1. Full renal work-up, including examination of urine sediment, discussion with renal team and then commence high dose corticosteroids and then, if further decline in renal function;
2. Renal biopsy, followed by plasmapheresis should be considered with close involvement of the renal team.

No enadenotucirev is to be administered after the development of proteinuria as this constitutes a DLT.

Refer to section 8.5 for guidance on dose modification/ interruption due to toxicity.

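### The dosing-day-3 dipstick and bloods may be taken before dose 2, so dose 3 can be given with no renal or laboratory result after dose 2

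*Protocol*

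**What the plan says.** Protocol 5.3 states that loading and post-loading doses "should be given on 3 non-consecutive days over a 7-day period during weeks 1-2-and 8-9", and gives Mon/Wed/Fri and Fri/Mon/Wed as examples. Its tables assign Schedule A, B, A to dosing days 1, 2, 3, both in weeks 1/2 (all groups) and in weeks 8/9 (groups 2 to 4).

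Under Schedule A (5.3.1), "the following assessments can be completed within 72 hours prior to the dose"; only vital signs are tied to the day of dosing. Schedule A contains the renal check: "Urine dipstick – if 2+ or greater proteinuria enadenotucirev dosing should be interrupted pending completion of 24 hour urine collection". It also contains haematology, biochemistry and coagulation. Schedule B (5.3.2) has a review of "Adverse events and DLTs since the previous assessment", medications, examination, vital signs, weight and ECOG status, but no dipstick and no bloods. The Summary Schedule of Events agrees. The post-dose evaluations in 5.4 list vital signs only.

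Section 1.2 describes two periods of renal effect. One is acute: "The first in the acute period following dosing (on Days 1, 3, 5) where proteinuria, reduction in albumin" and reduced renal function are reported, recovering over time. The other is later: "In some subjects, similar findings occur around Day 21 onwards". Section 9.3 states: "No enadenotucirev is to be administered after the development of proteinuria as this constitutes a DLT".

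**The concern.** The dosing-day-1 tests precede the first dose of a sequence, so the dosing-day-3 tests are the only scheduled dipstick and bloods after the sequence has started and before its last dose. If they may be drawn before dose 2, they need not show anything about dose 2.

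In groups 3 and 4, dose 2 is the first 3 x 10^12 vp dose of the sequence (8.2). Section 9.2 lists treatment-related proteinuria in 0% of patients at 1 x 10^12 and 20% at 3 x 10^12, without grade. The renal DLT in 9.1 rests on urinalysis with confirmation, or on eGFR, so neither Schedule B nor vital signs can reveal it. The bar in 9.3 can act only on a result that exists.

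DLT is a primary endpoint. Under SAP 6.2.1, a patient who completes treatment and the 13-week window with no recorded DLT enters the toxicity model as a full-weight non-DLT.

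**Working it through.** **1. Window against dose spacing.** Inputs: the 72 h window (5.3.1) and three non-consecutive days within seven (5.3). Taking doses at the same clock time, the window for dose 3 opens (72 h minus the dose 2-to-3 gap) before dose 2. With the first dose on day 1 there are six permitted patterns:

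| Dosing days | Gap, dose 2 to 3 | Window opens |
|---|---|---|
| 1-3-5 (Mon/Wed/Fri) | 48 h | 24 h before dose 2 |
| 1-4-6 (Fri/Mon/Wed) | 48 h | 24 h before dose 2 |
| 1-5-7 | 48 h | 24 h before dose 2 |
| 1-3-6 | 72 h | at dose 2 |
| 1-4-7 | 72 h | at dose 2 |
| 1-3-7 | 96 h | 24 h after dose 2 |

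Three of six are exposed, including both named examples. For Mon/Wed/Fri, Friday minus 72 h is Tuesday, before the Wednesday dose. The gap from dose 1 to dose 3 is at least 96 h, so the sample always follows dose 1.

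Group 4 in week 3 is not exposed: "Doses given during the 1 st week of chemoradiation should be given on day 1 and day 5", which is 96 h apart, with Schedule A before both.

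**2. When the next scheduled tests fall.** Take week 1 day 1 as a Monday and call it day 1.

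- After loading, the next tests are at week 3 day 1 (day 15). Mon/Wed/Fri ends on day 5: 15 - 5 = 10 days. Fri/Mon/Wed ends on day 10: 15 - 10 = 5 days. If that sample is also drawn 72 h early, these become 7 and 2 days.
- After maintenance, the next tests are at week 13 (days 85-89, +/- 3 days, so 82-92). Mon/Wed/Fri in week 8 ends on day 54: 28 to 38 days. Fri/Mon/Wed ends on day 59: 23 to 33 days.

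The exposure is therefore mainly in weeks 8/9. After loading, a persistent abnormality should appear at week 3 day 1.

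**3. What one unrecorded DLT does to the toxicity model.** Inputs from SAP 6.2.1:

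- dose codes 1, 2, 4, 6, with reference 6;
- logit(p) = log(alpha) + beta x log(x/6), read as an inverse-logit probability;
- log(alpha) ~ N(log(0.3/0.7), 1.44) and log(beta) ~ N(-0.1, 0.25), independent;
- safety criterion P(p > 0.35) < 0.35, then the highest posterior probability of p in (0.2, 0.35).

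I assume complete data (all weights 1) and no DLTs on schedules 1 and 2. The posterior was computed on a grid; figures are good to about 0.01.

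| Patients on schedules 1/2/3 | P(p > 0.35) at schedule 4, one DLT on schedule 3 counted | Same, DLT missed | Toxicity model recommends (counted; missed) |
|---|---|---|---|
| 2/2/2 | 0.43 | 0.15 | 3; 4 |
| 2/2/3 | 0.35 (on the limit) | 0.12 | 3; 4 |
| 2/2/4 | 0.29 | lower | 4; 4 |
| 2/3/3 | 0.32 | lower | 4; 4 |
| 3/3/3 | 0.31 | lower | 4; 4 |

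Two patients per schedule is the smallest number from which the escalation rule (at least two patients on the dose below for at least 8 weeks) can reach schedule 4. The recommendation changes at that size and, marginally, at 2/2/3. It does not change in the three larger configurations.

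**The case against.** The strongest reply is that clinical surveillance is not interrupted. The Schedule of Events marks AE and DLT assessments on all three dosing days, section 12 requires review before each administration of enadenotucirev, and every dose has post-dose vital signs. That stands, and it limits the point to the dipstick and bloods. Section 5.3 also says its assessments are required on each dosing day, but 5.3.1 expressly relaxes this, and no text requires the dosing-day-3 sample to follow dose 2.

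Some laboratory DLTs are defined by duration (ALT/AST above 5 x ULN for 8 days or more; grade 4 neutropenia for 7 days or more). For these, moving one sample by a day or two matters little. That also stands; the point concerns abnormalities that resolve between checks.

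A reader might infer more than the documents support:

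- *That both renal periods go unobserved.* After loading, Day 21 falls around weeks 3-4, and Schedule A is done at week 3 day 1 and weekly in weeks 4 to 7. After maintenance, week 13 samples the later period late, but does sample it.
- *That DLT rates on higher schedules are biased low in general.* Section 1.2 says the later renal effects seem unrelated to dose or schedule, and that most renal findings were not judged clinically significant or reported as adverse events. The 20% proteinuria figure is an adverse-event rate; no rate at DLT level is given.
- *That 5.3.1 directly contradicts 9.3.* It does not permit dosing over detected proteinuria. It allows the detecting test to be taken too early to inform that decision.
- *That the change in recommendation measures this defect.* Any missed DLT would have the same effect, and only in very small cohorts.

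**Conclusion.** The point holds in a limited form. In three of six permitted patterns, including both that the protocol names, a site following the text exactly can give dose 3 of a loading or maintenance sequence with no dipstick, creatinine or transaminase result after dose 2. This undercuts the purpose of the dosing-day-3 tests and of the bar in 9.3. A transient renal or laboratory DLT can go unrecorded, chiefly in weeks 8/9, where 23 to 38 days pass before the next scheduled tests.

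The 72 h and 96 h gaps and group 4 week 3 are not exposed. The documents do not say how often sites would sample before dose 2, or how often a DLT-level abnormality would resolve unseen, so the frequency of missed DLTs cannot be estimated. The effect on escalation is an illustration that rests on assumed, complete data. It shows that one missed event can matter at 2/2/2 patients, not that it usually would. It concerns the toxicity model alone: the schedule given is the lower of the toxicity and efficacy recommendations, and the TMG may choose a lower one.

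**What to change.** The sponsor should reconcile Protocol 5.3 (dose spacing and the statement that assessments are required on each dosing day), 5.3.1 (the 72-hour window), 9.3 (no dosing after proteinuria), section 12 (review before each administration) and the Summary Schedule of Events. The aim is that the dosing-day-3 Schedule A dipstick and bloods serve as a check on dose 2 in every permitted dosing pattern. The exact timing rule is for the sponsor to set.

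This is a wording change to tests already scheduled; it adds no visit and no sample. The cost is faster turnaround of results for dosing day 3 at sites that now sample early. No change to the SAP model is needed.
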